6.2.2.4 Toxicology

Nonclinical safety assessments of MEN1309 established that the cynomolgus monkey (*Macaca fascicularis*) was a relevant animal species. The data confirmed the following similarities between cynomolgus monkey and human: (i) high homology between the human and cynomolgus CD205 protein sequence (by BLAST search), (ii) a similar target antigen expression profile in tissues and white blood cells of monkey and human, (iii) comparable binding affinity of the MEN1309 antibody for the human and monkey CD205 antigen (by enzyme-linked immunosorbent assay [ELISA]) and (iv) similar receptor occupancy levels on human and monkey white blood cells (by Fluorescence-Activated Cell Sorting [FACS]).

Toxicity studies were conducted evaluating MEN1309 doses levels ranging from 0.1 to 5 mg/kg following single and repeat-dose administration in exploratory (non-Good Laboratory Practice [GLP]) and pivotal (GLP) studies. During the single and repeated toxicology study in Non-Human Primate (NHP), evidence of transitory skin inflammatory reactions (reddening, peeling and wound) were observed at injection/sampling sites and in other cutaneous areas. Global histopathology reports judged all these skin side effects as possibly non-treatment related.

In the course of toxicological studies in NHP, no evidence for substantial cytokine release following MEN1309 administration has been detected.

A shortening of QT-interval and QTc-interval duration was noted on Day 1 in females receiving MEN1309 at 5 mg/kg. The clinical relevance of QT shortening and potential risk of arrhythmias has not been demonstrated (7).

In the toxicology studies, decreases in white blood cells at 1 week following dose administration, particularly neutrophils and lymphocytes, and regenerative anemia were observed which recovered by Day 22, prior to the next dose administration. On the basis of these haematological toxicities, the No Observed Adverse Effect Level (NOAEL) was 0.3 mg/kg and the Highest Non-Severely Toxic Dose (HNSTD) was 1.0 mg/kg MEN1309 following repeat-dose administration at a 3-week interval.

6.2.2.4.1 Cross-reactivity of MEN1309 with human tissues

Tissue Cross Reactivity (TCR) was carried out in 33 different frozen human and cynomolgus monkey tissues. In both species examined, specific membranous/granular cytoplasmic staining of mononuclear cells was observed in lymphoid tissues, as well as in mucosa-associated lymphoid nodules in several organs. Overall, tissue and cellular distribution of this membranous staining was characteristic of the known expression of the targeted antigen (CD205) in various cell types of the immune system, such as dendritic cells, B cells, and CD8+ lymphocytes.

In some human donors, cytoplasmic staining in various glandular or mucosal epithelial cells in breast, colon, lung, thyroid follicles, ureter, uterine cervix and endometrium, and fallopian tube sections was observed, as previously reported. Similar findings were observed for almost the same monkey tissues.

6.2.2.4.2 In vitro cytokine release (human whole blood)

The potential of MEN1309 to elicit cytokine responses in human whole blood collected from 24 healthy donors was compared to commercial therapeutic antibodies. The MEN1309 cytokine release profile was largely similar to [REDACTED] even if in the same donors, at the same concentration of antibody, responses to reference antibodies were lower than those observed with MEN1309. In most donors, MEN1309 induced release of mainly interleukin (IL)-6; in a few donors, release of IL-8, tumor necrosis factor (TNF)-alpha, IL-1beta, IL-10 was observed.

6.2.2.4.3 *In vitro red blood cell haemolysis test*

The clinical dose form of MEN1309 at the concentrations of 1000, 300, 100, and 30.0 $\mu\text{g}/\text{mL}$ was not shown to induce haemolysis in blood samples from healthy male donors.

6.2.3 Clinical Experience

The Step 1 (dose escalation in solid tumors) of the MEN1309-01 study, aiming to determine the MTD of MEN1309 in patients with CD205-positive advanced solid tumors is currently ongoing. The first patient has been treated on Oct 03rd, 2017. At the time Protocol Version 3.0 is issued, the dose cohort of 1.60 mg/kg has been successfully completed in Step 1, according to an ATD. As per protocol, the study design changed to an ascending dose cohort of 3+3 upon the occurrence of a DLT of febrile neutropenia which was observed in the first patients treated at 1.60 mg/kg. Consequently, this cohort has been expanded to six patients that have been treated and completed the DLT assessment period. Neutropenia grade 3/4 lasting \leq 7 days (and therefore not qualifying as DLT) was observed in all patient treated at 1.60 mg/kg as the only safety signal of clinical relevance; therefore the next cohort at 2.40 mg/kg dose level (i.e. with 50% higher ascending dose as per CRC decision) is open.

Considering that the dose cohort of 1.60 mg/kg has been successfully completed in Step 1, the first cohort of patients in Step 2 (dose escalation in NHL) is proposed to be open at 0.80 mg/kg (to be confirmed by the CRC).

6.2.4 Translational model-based strategy to support the choice of clinical doses for the first in human study

A translational model-based analysis has also been carried out to support the dosing regimen for the FIH clinical study. Allometric approaches were applied to (i) the monkey PK data to predict the human PK profile; (ii) a population PK/PD model, developed to scale the time-course of MEN 1309-induced neutropenia from monkey to patients; (iii) tumor growth inhibition data in mice, to identify the potential clinical effective dosing regimens. The risk-benefit profile of the proposed dosing schedule was evaluated based on predicted neutropenia and expected antitumor activity in patients.

This translational analysis supports the selected dosing regimen for the FIH study, namely the anticipated therapeutic dose range (ATDR) with 100% dose escalations from 0.05 to 6.4 mg/kg.

6.2.5 Rationale for a Phase I Study and Selection of the Starting Dose

In order to identify the starting dose for the first administration in humans, nonclinical safety assessments of MEN1309 were conducted in a single relevant species, the NHP (§6.2.2.4).

The starting dose for a phase I clinical study in oncology may be defined as 1/6th of the HNSTD (8). One sixth of the MEN1309 HNSTD of 1 mg/kg equals a dose of 0.16 mg/kg. However, taking into account the novelty of the antigen and the intrinsic potency of ADCs, the Sponsor intends to have a more conservative approach applying an additional 3-fold safety factor; thus, the proposed starting dose is 0.05 mg/kg.

A PK model was developed from the PK and TK data obtained in monkeys; drug exposures in humans were simulated on a body weight allometric basis using the model parameters. A comparison of the observed exposures in monkey and the predicted exposure at the proposed starting dose in humans is provided in the Table 1:

Table 1: Comparative exposure to MEN1309 in monkey and humans

| Species | Dose definition | Dose level (mg/kg) | Infusion length (hr) | C _{max} (µg/mL) | AUC µg* hr/mL | Exposure wrt starting dose | |
|---------|-----------------|--------------------|----------------------|--------------------------|---------------|----------------------------|---------|
| | | | | | | C _{max} | AUC |
| Monkey | HNSTD | 1 | 1 | 23.61 | 438.5 | 35.2 x | 151.2 x |
| | NOAEL | 0.3 | 1 | 6.45 | 44.2 | 9.6 x | 15.2 x |
| Human | Starting | 0.05 | 3 | 0.671 | 2.9 | 1 x | 1 x |

At the proposed starting dose-level of 0.05 mg/kg in humans, the predicted exposure was a C_{max} of less than 1 µg/mL and an AUC of 2.9 µg*hr/mL. This exposure was anticipated to be 35-fold (C_{max}) and 151-fold (AUC) lower than that at the HNSTD and 10-fold (C_{max}) and 15-fold (AUC) lower than that at the NOAEL. Furthermore, at the proposed starting dose C_{max} concentration (1 µg/mL MEN1309), CD205 receptor occupancy was estimated to be approximately 20-50% on human white blood cells as determined ex-vivo by FACS.

Thus, taking together a pharmacological approach integrated with the toxicity exposure response relationship data in monkeys, the proposed starting dose in humans of 0.05 mg/kg MEN1309 was expected to provide an adequate safety margin for patients with advanced cancer.

6.3 RISK BENEFIT ASSESSMENT

Treatment options for metastatic solid tumor and NHL either with unfavorable prognosis according to international scoring systems or refractory/relapsed, is still highly unsatisfactory.

MEN1309 is an ADC, targeting the CD205 antigen largely expressed in both solid tumors and NHL which has shown a potent cytotoxic activity in vitro and vivo models.

The benefit of MEN1309 is unknown since this is the first administration of MEN1309; however its potential is supported by the recent evidence provided by a similar therapeutic approach of two drugs, namely trastuzumab-DM (Kadcyla®) in metastatic HER2+ breast cancer, as well as

brentuximab- vedotin (Adcetris®) in relapsed/refractory Hodgkin lymphomas and ALCL, which have greatly improved the management of such diseases, prolonging PFS and OS.

Considering the lack of standard therapeutic options for the selected patient populations, and the pharmacological properties and acceptable toxicological profile shown in preclinical studies, MEN1309 can represent a new targeted therapeutic opportunity in pre-treated metastatic solid tumors and in refractory/relapsed NHL patients for whom no highly effective standard treatment is currently available.

In this study, MEN1309 treatment will be continued until objective disease progression is documented or another criterion for discontinuation (e.g., toxicity, withdrawal of consent) is met for patients affected by solid tumors; while for patients affected by NHL, MEN1309 administration will be allowed until objective disease progression up to 8 cycles or to maximum tolerability; beyond the 8th cycle further cycles might be allowed for patients who still benefit from the treatment based upon Investigator's judgment and medical monitoring approval.

To mitigate the risk of the FIH administration and to guarantee patients' safety during the study participation, the following measures have been applied in accordance with EMA guidelines (9, 10) and have been updated considering the experience gained up to the dose of 1.60 mg/kg in the FIH MEN1309-01 study:

- 1) A starting dose of 0.05 mg/kg which offers a safety factor of 20 to the HNSTD, i.e., higher than the standard safety factor of 6. Moreover, based on allometric PK model, the predicted C_{max} and AUC in human is 35-fold (C_{max}) and 151-fold (AUC) lower than that at the HNSTD. This starting dose was appropriate since no related AEs higher than grade 1 have been observed up to the 0.80 mg/kg in Cohort 5 during DLT observation period;
- 2) In order to mitigate the potential risk of severe and fast progressing infusion reactions, the 1-hour infusion tested in preclinical animal model has been prolonged to 3 hours (up to 6 hours after interruption), with no influence on the expected effective exposure as suggested by PK modelling predictions. Furthermore, mandatory premedication is required, including an antihistamine and an antipyretic, as per local practice, and dexamethasone 20 mg to be administered within 30 to 60 minutes prior to study drug administration. No infusion related reactions have been observed in the first six dose cohorts up to 1.60 mg/kg; thus -under the condition foreseen by the protocol- the risk for infusion reaction remains limited;
- 3) According to PK/PD model-based predictions (data on file), the neutropenia-related risk, as reported in toxicity studies in monkey, is expected to be manageable in humans. The initial data collected during the dose escalation confirmed that neutropenia is the most frequent adverse reaction with MEN1309 (one DLT observed; and six grade 3/4 neutropenia); however up to 1.60 mg/kg dose neutropenia lasted \leq 7 days with spontaneous recovery. Follow-up of neutrophils count value and recovery time-course will be closely monitored in the subsequent cohort(s) of patients by including extra haematological tests prior and before the currently observed nadir of Day 15. If neutropenia will be established as the main limiting toxicity for MEN1309, the CRC - in accordance with the CRC charter, stating that CRC is in charge to drive "any adjustment in premedication and concomitant medication" - will drive the mandatory use, if appropriate, of grow factor support; For the proposed dosing schedule, PK/PD modelling predicts complete recovery from neutropenia for the majority of the patient population, thereby supporting the adequacy of a 21-day inter-dosing interval;
- 4) Although MEN1309 did not show any ocular toxicity during toxicology studies in monkeys, due to the potential for ocular adverse effects with this class of drugs (ADC-DM4), patients with any active or chronic corneal disorder or Sjogren's syndrome are excluded from the study. Furthermore, ophthalmic visits shall be performed and - in case of the occurrence of ophthalmic events higher than grade 1 during the study treatment period - repeated bi-

weekly (or even more frequently, if indicated). A summary of eye disorders reported following the treatment with ADC is listed in Appendix IV as reference.

- 5) A minimum 7-day stagger is required to progress with the dose escalation as well as to expand the number of patients within each dose level; this stagger will allow the evaluation/interpretation of any adverse events/reactions prior to expose other patients to the same dose/higher doses of MEN1309;
- 6) Although MEN1309 did not show any ocular toxicity during toxicology studies in monkeys, due to the potential for ocular adverse effects with this class of drugs (ADC-DM4), patients with any active or chronic corneal disorder or Sjogren's syndrome are excluded from the study. Furthermore, ophthalmic visits shall be performed and - in case of the occurrence of ophthalmic events higher than grade 1 during the study treatment period - repeated bi-weekly (or even more frequently, if indicated). A summary of eye disorders reported following the treatment with ADC is listed in Appendix IV as reference.
- 7) Regarding skin toxicity during the single and repeated toxicology study in NHP, evidence of transitory skin inflammatory reactions (reddening, peeling, and wound) were observed at injection/sampling sites and in other cutaneous areas. In order to mitigate the potential risk of skin toxicity, patients with any ongoing acute inflammatory skin disease or chronic skin disease not controlled by specific treatment are excluded from the study; moreover, a dermatologic visit shall be performed and - in case of the occurrence of dermatological events higher than grade 1 during the study treatment period - repeated bi-weekly (or even more frequently, if indicated);
- 8) MEN1309 absorption spectrum is largely below 290 nm, although a Molar Extinction Coefficient (MEC) greater than 1000 L mol⁻¹ cm⁻¹ is observed up to 290-295 nm. Thus according to IHC S10 and studies conducted with ADCs containing DM4, MEN1309 is anticipated to have a very limited, if any, potential for phototoxicity. The risk for skin and ocular reactions -although very unlikely to occur- cannot be ruled out thus any skin and ocular reactions will be carefully monitored as mentioned above. In addition patients will be informed to avoid sun over-exposure and to adopt protective measures (§8.4.8);
- 9) A shortening of QT-interval and QTc-interval duration was noted in the single dose toxicology monkey study on Day 1 in females receiving MEN1309 at 5 mg/kg. It is doubtful the clinical relevance of a QT shortening and its association with a risk of arrhythmias has

not been demonstrated (7); nevertheless patients with diagnosis of short and long QT syndrome, history of clinically significant atrial arrhythmia (including clinically significant bradyarrhythmia), as determined by the treating physician and any history of ventricular arrhythmia are not eligible to participate to the study. In addition, ECG will be monitored during the IV infusion up to 30 minutes after end of infusion;

10) DM-4 as other maytansine derivatives are reported to cause neuropathy; for this reason patients with neuropathy grade ≥ 2 are not eligible to participate to the study;

11) The propensity of new targeted treatment such ADCs to cause TLS has not been systematically examined. Therefore, to prevent such potential risk before treatment initiation, TLS risk assessment and TLS prophylaxis is recommended when appropriate, (see Appendix II);

12) Patients must be treated and monitored at Cycle 1 as in-patients for 48 hours following drug administration; this measure allows for a strict monitoring of safety laboratory tests as well as of vital signs, ECG and recording of any adverse events. In addition, the administration of the investigational drug should only be carried out in a facility in which resuscitation equipment and medical personnel trained in the treatment of anaphylaxis and TLS are immediately available;

13) Based on literature data, the risk of drug-drug interaction (DDI) is very low although the lack of DDI studies does not allow to completely rule out the potential interaction of DM4 and its metabolite S-methyl-DM4 with P450 isoforms CYP3A4, CYP3A5 and CYP2D6 as well as with P-gp after MEN1309 administration. Therefore, the risk/benefit of MEN1309 in patients under treatment with inhibitors (weak, moderate and strong) and substrates of CYP3A4/5, CYP2D6 and P-gp shall be considered in the light of the potential DDI and consequent toxicity (§8.4.8);

14) A CRC consisting of the Principal Investigators and the Sponsor's qualified Medical Representatives (and invited experts, when needed) will regularly review the safety, PK, and PD data, as defined by the CRC charter. Specifically, in both Step 1 and Step 2, the CRC will assess all available data at the end of each dose-level, and will confirm the dose escalations as per protocol or for any adjustment needed. In addition the CRC has the duty to drive any adjustment in premedication and concomitant medication. The CRC decisions

will be immediately implemented and notify to the CA/EC, when appropriate. At the time the Step 2 starts, the CRC will include investigators experts in the field of NHL.

7. STUDY OBJECTIVES

7.1 PRIMARY OBJECTIVES

- To identify the MTD of MEN1309 when given as an IV infusion on Day 1 of a 21-day cycle in patients affected by CD205-positive solid tumors and NHL.
- To identify the DLT of MEN1309.

7.2 SECONDARY OBJECTIVES

- To assess the toxicity profile of MEN1309.
- To assess the pharmacokinetic profile after single and repeated doses of MEN1309 following IV administration.
- To determine the immunogenicity of MEN1309.
- To determine the preliminary clinical activity of MEN1309.

7.3 EXPLORATORY OBJECTIVES

- To determine the correlation between free CD205 with the clinical activity of MEN1309.
- To determine the correlation between CD205 expression on FFPE archived tissues samples and/or derived from new tumor biopsies and clinical activity of MEN1309.
- To determine the DNA sequence of CD205 at baseline.
- To determine CD205 expression by flow cytometry on peripheral blood cells at baseline.

8. INVESTIGATIONAL PLAN

8.1 OVERALL STUDY DESIGN AND PLAN DESCRIPTION

This study is designed as an open label, multicenter, dose escalating, FIH study to be conducted in approximately 8 EU sites. Taking into consideration that only patients with CD205 positive tumors are eligible, a limited number of sites with experience in the conduction of FIH studies have been selected for trial participation and are expected to adequately contribute to the patients recruitment, in particular when the dose cohorts have to be expanded.

The study design is in agreement with the current regulatory European Medicines Agency guidelines regarding the evaluation of anticancer medicinal products in man (11, 12). The overall study design is shown in §2.1, with the plan of study procedures tabulated in § 2.2, 2.3 and 2.4.

The study will consist of 2 steps.

Step 1 aims to establish the DLT and MTD of MEN1309 in patients with CD205-positive advanced solid tumors, with dose escalation starting with 1 single patient per cohort and double dose steps per dose level (ATD) until grade ≥ 2 drug-related toxicity is observed during the DLT assessment window in the 21-day period following the first administration of MEN1309.

Upon occurrence of grade ≥ 2 drug-related toxicity, the dose escalation has to follow a modified Fibonacci sequence in which the dose increments become smaller as the dose increases (i.e., dose-increase by 67%, 50%, 40%, and 35% of the preceding doses) and a minimum of 3 patients per cohort are to be enrolled, with a minimum 7-day stagger between patients. Any cohort in which 1 patient experiences a DLT during the DLT assessment window (the 21-day period following the first administration of MEN1309) will be expanded up to 6 patients (with a minimum 24 hours stagger between the 3 additional patients).

Step 2 aims to establish the DLT and MTD of MEN1309 in patients with CD205-positive NHL following the dose escalation based upon experience gained during Step 1 in solid tumors.

Step 2 is intended to run in parallel with Step 1 but at a lower dose level, so that the cohorts of patients with NHL in Step 2 cannot exceed at any time the doses tested in solid tumors during the dose escalation.

MEN1309-01 cohorts will potentially run in parallel at the same dose level only at the time the MTD is to be confirmed in the expansion cohort of patients in Step 1 and Step 2.

At the time Protocol Version 3.0 is running, the dose cohort of 1.60 mg/kg has been successfully completed in Step 1, therefore the dose escalation in Step 2 will start at 0.80 mg/kg (or at lower level as per decision of the CRC).

In both Step 1 and Step 2, if 2 or more patients experience a DLT at any dose level, further enrolment at that dose level and further dose escalation will cease, and the previous dose level will be defined as the MTD. However, if ≥ 2 DLTs occur during the dose escalation, an intermediate dose level can be evaluated prior to defining the previous dose level as MTD. Upon MTD definition, the MTD cohort in both Step 1 and Step 2 will be expanded up to a total of 10 patients to further explore the safety profile of MEN1309.

In both Step 1 or Step 2, each dose level escalation (or de-escalation) at the pre-defined dose level of MEN1309 or at any intermediate dose levels will be subject to the assessment of the CRC which consists of the Principal Investigators and the Sponsor's qualified Medical Representatives (and invited experts when needed). In addition the CRC has the duty to drive any adjustment in premedication and concomitant medication. The CRC decisions will be immediately implemented and notify to the CA/EC, when appropriate. At the time the Step 2 is open, the CRC will include investigators who are experts in the field of NHL.

The overall study duration will depend on the number of escalating dose levels/cohorts and the number of patients by cohort, as described in the above sections.

All patients will undergo a 12-week Pre-Screening Period followed by a 4-week Screening Period. The Pre-screening Period in patients who are CD205 positive can be extended up to the time they undergo the Screening Visit.

Each treatment cycle will last approximately 3 weeks.

Individual study duration will depend on the duration of study treatment which continues up to disease progression for solid tumors and up to 8 cycles for NHL (further cycles beyond the 8th cycle may be allowed for patients who still benefit from the treatment based upon the Investigator's medical judgement and medical monitor approval).

The End of Study Visit will be performed within 6 weeks after the last administered dose or at the time of study withdrawal/treatment discontinuation of study drug.

After the End of Study Visit, all patients evaluable for efficacy will be followed for survival status according to local practice (a visit or a telephone call) every 12 weeks up to a period of 12 months after first treatment administration to the last patient.

The study ends 12 months after first treatment administration to the last patient.

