8.2.3 Withdrawal of patients from study or discontinuation of study drug

Participation in the study is strictly voluntary and patients have the right to withdraw from the study at any time without explanation. This will not affect their rights for future medical care.

Patients may also be discontinued from study drug at the Investigator's discretion or at specific Sponsor's request at any time. Patients will be withdrawn from the study if they experience:

- Protocol violation (e.g., prohibited medication, poor compliance with study procedures/treatment).
- Disease progression.
- DLT at Cycle 1.
- Occurrence of any of the ADR criteria qualifying for DLT at any Cycle following Cycle 1.
- Life threatening related Serious Adverse Event (SAE).
- Patient receives other treatment for solid tumors or lymphoma.
- Occurrence of pregnancy.
- Patient's request.

NOTE: Patients who experienced DLT might be allowed to continue on study at a lower dose if considered beneficial by the investigator and after approval by the Sponsor.

All patients shall undergo the End of Study Visit at the time of study withdrawal or discontinuation of study drug. Unscheduled assessments showing disease progression and leading to patient's withdrawal can replace the End of Study Visit provided that all assessment/procedures scheduled for this visit are completed.

If a patient prematurely terminates the study as per patient's request, data already collected will be used and analyzed for the purpose of the study, as per local regulation.

In case of withdrawal of consent, the patient may choose if samples/images which are already collected but not analysed yet, can be analysed or shall be destroyed.

During escalation phase, patients not evaluable per DLT will be replaced.

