8.5.5 Study Endpoints

8.5.5.1 Primary Endpoint

Identification of MTD, defined as the highest dose level at which no more than 1 of 6 patients experiences a DLT during the DLT assessment window. In case the prophylactic use of growth factor support is made mandatory by the CRC, MTD with growth factor support will be established. **Identification of DLT**, defined as any of the following adverse drug reactions (ADRs) that will be assessed during Cycle 1:

- any grade ≥ 3 cardiac toxicity, new segmental wall-motion abnormalities, or cardiac troponin I or T elevation of grade 3 or higher;
- any grade ≥ 3 elevations in total bilirubin, hepatic transaminases, or ALP levels; in patients with baseline grade 2 hepatic transaminase or ALP levels, an elevation to $\geq 10 \times$ ULN is considered a DLT;
- any grade 3 non-haematologic toxicity lasting > 7 days, (excluding diarrhea/nausea for which no adequate and optimal therapy has been implemented and alopecia);
- any grade 3 vomiting lasting > 3 days despite adequate and optimal therapy;
- any grade ≥ 4 non-haematologic toxicity;
- any grade 4 thrombocytopenia or anemia;
- any grade 4 neutropenia lasting > 7 days or febrile neutropenia;
- any treatment delay of > 2 weeks because of delayed recovery from toxicity related to MEN1309 (except for alopecia).

In case neutropenia will be established as the only DLT, the study will continue with the assessment of DLT of MEN1309 given together with routine prophylaxis with growth factors.

Upon the prophylactic use of growth factor support for neutropenia is made mandatory by the CRC, the DLT criterion related to grade 4 neutropenia will change as follows:

- any grade 4 neutropenia lasting > 5 days or febrile neutropenia despite the use of growth factor support.

Although dose escalation is primarily based on the incidence of DLTs during Cycle 1, toxicities that

meet criteria for DLTs and are observed during Cycle 2 or subsequent cycles are also taken into account for the assessment of toxicity and definition of MTD.

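### A Step 1 dose above 1.60 mg/kg cleared at 0/3 can be named the MTD before it meets the endpoint's limit of 1 DLT in 6, and the planned confirmation in expansion has no criterion

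*Protocol*

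**What the plan says.** **Definition.** Protocol 8.5.5.1 has the MTD "defined as the highest dose level at which no more than 1 of 6 patients experiences a DLT during the DLT assessment window". SAP 5.1.1.1 gives the same definition.

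**Operating rule.** Protocol 8.1 says that "if 2 or more patients experience a DLT at any dose level, further enrolment at that dose level and further dose escalation will cease", and then that "the previous dose level will be defined as the MTD". Protocol 8.4.3 and SAP 3.1.1.1 repeat this. None of the three sets a minimum number of patients at the previous dose.

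**Cohort size.** After the accelerated phase, "a minimum of 3 patients per cohort are to be enrolled". Under Protocol 8.1 and 8.4.2 a cohort goes to six only when one of its own patients has a DLT.

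**Routes that can delay or change the naming.**
- After 2 or more DLTs during escalation, "an intermediate dose level can be evaluated prior to defining the previous dose level as MTD".
- The CRC reviews every escalation and de-escalation (Protocol 8.1, 8.7).
- If neutropenia proves to be the only DLT, DLT assessment continues with routine growth-factor prophylaxis, and an MTD with that support is established (Protocol 8.5.5.1).

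**After naming.** In Protocol 8.1, "the MTD cohort in both Step 1 and Step 2 will be expanded up to a total of 10 patients". The same section and 8.4.3 refer to the MTD being confirmed in the expansion cohorts, without saying what result confirms it. On replacement, Protocol 8.2.3 says: "During escalation phase, patients not evaluable per DLT will be replaced". Protocol 9.2 and SAP 6.1.1.3 also limit replacement to escalation.

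**Where Step 1 stood.** Protocol 6.2.3 reports one DLT at 1.60 mg/kg, after which "this cohort has been expanded to six patients that have been treated and completed the DLT assessment period". The next cohort is 2.40 mg/kg. The SAP Introduction gives Step 1 doses up to 3.36 mg/kg.

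**The concern.** The definition asks for six patients, but the rule that applies the label can act on three. A dose cleared at 0/3 becomes the MTD through what happens at the dose above it, and the text does not require it to be filled to six first. The primary endpoint could then be declared, and expansion opened, at a dose that does not yet satisfy the endpoint's own wording. If the expansion stopped early, or its patients were not DLT-evaluable, the label could stay without six evaluable patients behind it.

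The exposure is in Step 1 above 1.60 mg/kg. The 1.60 mg/kg dose already has six patients with one DLT, so it meets the definition if 2.40 mg/kg fails.

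**Working it through.** **Path under the rule.** The plan's own doses fit its step sizes: 1.60 × 1.50 = 2.40 and 2.40 × 1.40 = 3.36 mg/kg. If 2.40 mg/kg shows 0/3 and 3.36 mg/kg shows 2 or more DLTs, the rule names 2.40 mg/kg on three patients. This is an illustration; neither document reports these results.

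**Inputs.** Cohorts of 3, going to 6 after one DLT, and a stop at 2 or more DLTs (Protocol 8.1, 8.4.2). The documents give no target DLT rate. I assume true rates p of 20%, 30%, 40% and 50% at the dose in question, and q = p + 0.10 to p + 0.20 at the next dose. I also assume cohorts of exactly three, no intermediate dose, no CRC override and no growth-factor branch.

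**Formulas.**
- A: cleared at 0/3 = (1−p)³
- B: next dose shows 2 or more DLTs = [3q²(1−q) + q³] + 3q(1−q)² × [1 − (1−q)³]
- C: 2 or more DLTs in three further patients at the named dose = 3p²(1−p) + p³. From 0/3, this is failure of the 1-in-6 limit.
- D: 2 or more DLTs in the seven patients from 3 to 10 = 1 − (1−p)⁷ − 7p(1−p)⁶

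| p | A | B | A×B: named at 0/3 | C | A×B×C: named and would fail at six | D |
|---|---|---|---|---|---|---|
| 20% | 0.512 | 0.506–0.691 | 0.26–0.35 | 0.104 | 0.027–0.037 | 0.42 |
| 30% | 0.343 | 0.691–0.828 | 0.24–0.28 | 0.216 | 0.051–0.061 | 0.67 |
| 40% | 0.216 | 0.828–0.918 | 0.18–0.20 | 0.352 | 0.063–0.070 | 0.84 |
| 50% | 0.125 | 0.918–0.968 | 0.11–0.12 | 0.500 | 0.057–0.060 | 0.94 |

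Worked line for p = 20%, q = 30%: 0.512 × 0.506 = 0.259, and 0.259 × 0.104 = 0.027.

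**How often 0/3 is the route.** A dose clears at 0/3, or at 1/3 followed by 0/3. The share at 0/3 is 1/(1 + 3p(1−p)²), which is 69% to 80% for p from 10% to 50%. At fixed rates the next dose's result does not depend on which route was taken, so the share is the same among named doses.

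**Precision.** Exact 95% intervals for the DLT rate are 0–71% at 0/3, 0–46% at 0/6 and 0.4–64% at 1/6.

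**The case against.** The strongest reply is that the protocol already treats the named dose as awaiting confirmation, since 8.1 and 8.4.3 say the MTD is to be confirmed in expansion. Other text supports this:
- The two-DLT rule applies at any dose level, and only the intermediate-dose exception is limited to escalation. That favours reading the rule as covering expansion too. On that reading, a dose that would fail at six is caught once three more evaluable patients are treated.
- Expansion is to be done, and six patients need only three evaluable out of seven planned. Protocol 8.1 and 8.4.2 use a limit of six and a total of six for the same rule, so the ceiling of 10 may simply be the target.
- The growth-factor branch matters here. The reported DLT at 1.60 mg/kg was febrile neutropenia, so two DLTs at the next dose need not lead to naming.
- DLT-type toxicity in later cycles also counts towards the MTD.

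Most of this stands, and it makes the problem smaller. It does not close it. No passage says what result confirms the MTD, or states outright that the two-DLT rule governs expansion. Expansion follows the naming, and replacement is stated for escalation only. The SAP keeps the naming rule but does not repeat the confirmation wording.

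A reader might go further and infer that the expansion lacks a workable DLT limit for 10 patients, or for the SAP's 25 triple-negative breast cancer patients, or that the SAP has no table of DLTs per evaluable patient. The documents do not support either claim. The protocol text for that expansion and the CRC charter are not among them, and the SAP's list of tables is not shown.

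**Conclusion.** The mismatch is real: the definition needs six patients and the naming rule does not. Its practical size is modest, and I rate it minor to moderate. The chance that a tested dose is cleared at 0/3, named, and would fail at six is about 0.03 to 0.07 before expansion. This rests on the assumed DLT rates and a next dose 10 to 20 points more toxic, and it ignores the intermediate-dose, CRC and growth-factor routes. If the two-DLT rule applies in expansion, a completed expansion to 10 would trigger it with probability 0.42 to 0.94, and so would catch many such doses.

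Three stronger conclusions might be drawn, and none follows:
- That 69% to 80% of named doses are wrong. That figure describes the usual path of a 3+3 scheme and is not an error rate.
- That the MTD was in fact declared on three patients. Neither document reports the 2.40 mg/kg result or says that the rule was triggered.
- That Step 2 is equally exposed. The rule covers it in principle, but the SAP Introduction reports one Step 2 patient by the end of the study.

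**What to change.** **Protocol 8.1 and 8.4.3, and SAP 3.1.1.1.** Call the previous dose a provisional MTD until six DLT-evaluable patients at that dose, under the same growth-factor policy, show at most one DLT. Count the first expansion patients (at most three) towards the six, and replace any who are not DLT-evaluable. Step down if 2 or more of the six have a DLT.

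**SAP reporting.** Report a dose as the MTD only if this condition is met. Otherwise say that it is not met, and give the DLT count, the number DLT-evaluable and the exact interval. This part still works if enrolment is over.

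**Cost.** Wording in two documents, one 21-day wait before the rest of the expansion, and possible replacements. The three patients are already within the planned expansion.

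**Effect.** The chance that a dose qualifies falls by A × C. At a true rate of 20% this is 0.512 × 0.104 = 0.053, from 70.9% to 65.5%. At 30% it is 0.343 × 0.216 = 0.074, from 49.4% to 42.0%. The reduction is exactly the doses that would have failed the stated definition.
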